7.3.3 Study Drug Discontinuation

7.3.3.1 Prior to Weaning or Discontinuing Study Drug

“Prior to wean” assessments will be collected after the dose has been maintained for at least 12 hours and no more than 1 hour prior to beginning to wean study drug. In the event that the subject

will continue on commercial Remodulin beyond Day 28, these assessments should take place on Day 28.

- Physical examination
- Vital signs (BP, RR, HR, Temp, SpO₂)
- OI assessment (as long as the subject is on mechanical ventilation and ABGs are obtained)
- FiO₂
- MAP (as long as the subject is on mechanical ventilation)
- Blood gases (ABG if possible, otherwise CBGs/VBGs)
- Clinical laboratory assessments (See Section 3.3.2.3)
- Echocardiogram
- NT-proBNP
- Collect PK sample (See Section 3.3.3 and Appendix 15.2)
- Record concomitant medications
- Record doses of inotropes
- Record AEs

7.3.3.2 Daily While Weaning Study Drug

The following will be collected every day while weaning study drug.

- Physical examination
- Vital signs (BP, RR, HR, Temp, SpO₂)
 - BP, HR, and SpO₂ will also be collected with each study drug dose change
- FiO₂
- MAP (if the subject is on mechanical ventilation)
- Record concomitant medications
 - Record doses of inotropes with each study drug dose change
- Record AEs

These assessments will not be performed in subjects who continue on commercial Remodulin beyond Day 28.

7.3.3.3 Study Drug Discontinuation

The following will be collected immediately (within 12 hours) after study drug discontinuation.

- Physical examination
- Vital signs (BP, RR, HR, Temp, SpO₂)
- FiO₂
- MAP (if the subject is on mechanical ventilation)

- Clinical laboratory assessments (See Section 3.3.2.3)
- NT-proBNP
- Blood gasses (if arterial access is not available, collect CBGs/VBGs)
- Record concomitant medications (until 48 hours after the subject has stopped receiving study drug)
 - Record doses of inotropes
- Record AEs

These assessments will not be performed in subjects who continue on commercial Remodulin beyond Day 28.

7.3.3.4 48 Hours after Study Drug Discontinuation

The following will be collected 48 hours \pm 4 hours after study drug discontinuation.

- Vital signs
- Clinical laboratory assessments (See Section 3.3.2.3)
- Echocardiogram
- Record concomitant medications (until 48 hours after the subject has stopped receiving study drug)
 - Record doses of inotropes
- Record AEs

These assessments will not be performed in subjects who continue on commercial Remodulin beyond Day 28.

7.3.4 Follow-up/End of Study

The following assessments will be conducted during a final assessment visit at the time of withdrawal from the study, hospital discharge, or at 4 weeks after discontinuing study drug, whichever comes first, for all subjects who receive study drug. In the event that a subject randomized to Remodulin will receive commercial Remodulin beyond Day 28, and the subject has not been discharged from the hospital or withdrawn from the study, these assessments should take place on Day 56.

- Physical exam including height and weight
- Vital signs (BP, RR, HR, Temp, SpO₂)
- Clinical laboratory assessments (See Section 3.3.2.3)
- Record AEs

Subjects with ongoing AEs at the time of hospital discharge will continue to be followed for their AEs until either resolution (or return to normal or Baseline values), until judged by the Investigator to no longer be clinically significant, or until 4 weeks after last dose of study drug.

8 STUDY TERMINATION

8.1 CRITERIA FOR SUBJECT WITHDRAWAL

A subject may be withdrawn from the study and/or study drug by the Investigator at any time for reasons including, but not limited to, the following:

- The subject's parent or legal guardian wishes to withdraw the subject from further participation.
- A serious or life-threatening AE occurs or the Investigator considers that it is necessary to discontinue study drug to protect the safety of the subject.
- The subject did not initiate study drug.

If a subject is discontinued from the study prematurely, the Investigator must complete all applicable eCRF records, including the End of Study Record for that subject. If study drug has been administered, the Investigator should make every effort to perform all scheduled evaluations. In the event that a subject discontinues study drug prematurely due to an AE, the subject will be followed until either the Investigator determines that the AE has resolved, it is no longer considered clinically significant, the subject is lost to further follow-up, or for 4 weeks after last dose of study drug.

SAEs will be followed by United Therapeutics Corporation Global Drug Safety until resolution, death, or the subject is lost to follow-up.

If withdrawal from study drug is warranted, the dose of study drug will be weaned until discontinued. Abrupt cessation of study drug will be avoided due to the risk of rebound pulmonary hypertension.

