- Post-treatment data will be collected until subject is withdrawn from the study, death, time of hospital discharge, or until 4 weeks after last dose of study drug, whichever comes first.
 - The following key assessments will occur at time of withdrawal from study, hospital discharge, or at 4 weeks after last dose of study drug, whichever comes first: physical exam, vital signs, and clinical laboratory assessments.
 - Additionally, time on mechanical ventilation, time on inhaled iNO, and time of initiation of EMCO (if applicable) will be recorded.
 - The subject's participation in the study will conclude at the time of hospital discharge, death, withdrawal from the study, or at 4 weeks after last dose of study drug, whichever comes first.
 - Subjects with ongoing AEs at the time of study withdrawal or hospital discharge will continue to be followed for their AEs until either resolution (or return to normal or Baseline values), until judged by the Investigator to no longer be clinically significant, or until 4 weeks after last dose of study drug. All SAEs will be followed until resolution, death, or the subject is lost to follow-up, even if they are ongoing more than 4 weeks after the last dose of study drug.

Statistical Considerations	Based on the systematic review of use of nitric oxide for respiratory failure in infants by Finer and Barrington, 57.9% (194/335) subjects in the control group had an outcome of death or requirement for EMCO. In this study, assuming 60% subjects in placebo group and 30% subjects in Remodulin group with an outcome of death, requirement for EMCO, or need for additional PAH therapy, we calculated that 66 subjects (33 subjects per treatment group) will have at least 80% power to show a significant difference in favor of Remodulin at alpha level of 0.05 (one-sided test).
-----------------------------------	--

Approximately seventy subjects are planned to be randomized (1:1) to either receive treatment with Remodulin or placebo on top of the standard of care.

Sponsor United Therapeutics Corp.
 [name]
 [name]
 [name]

TABLE OF CONTENTS

LIST OF CONTACTS FOR STUDY	2
INVESTIGATOR'S AGREEMENT	3
PROTOCOL SYNOPSIS	4
TABLE OF CONTENTS.....	10
Table of In-text Tables.....	14
Table of In-text Figures	14
LIST OF ABBREVIATIONS	15
1 BACKGROUND AND RATIONALE	17
1.1 DEFINITION OF CLINICAL PROBLEM.....	17
1.2 REMODULIN (TREPROSTINIL) BACKGROUND	18

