^bThe Day 4 and the 72 hour time point assessment will fall on the same calendar day. A separate set of assessments should be captured for the Day 4 assessment. Day 7 and Day 14 assessments should be performed even if the subject has discontinued study drug. If subjects are discharged from the hospital prior to study Day 14, Day 14 assessments should be completed prior to hospital discharge. Subjects may receive up to 28 days of study drug.

^cHospital discharge or 4 weeks after discontinuation of study drug (whichever comes first).

^dVital signs include BP, HR, RR, temperature, and SpO₂. SpO₂ will be collected both pre- and post-ductal for the first 72 hours. BP, HR, and SpO₂ will be collected with each study drug dose change.

^eOI will be calculated as long as the subject is on mechanical ventilation and arterial blood gasses (ABGs) are collected.

^fCollected for as long as the subject is on mechanical ventilation.

^gABGs will be collected as long as the subject has arterial access. Venous or capillary blood gas will be collected thereafter. Lactate will be drawn with each blood gas.

^hClinical labs include: chemistries, hematology, and liver function tests. Performed by institutional laboratory.

ⁱIf subject had historic ECHO performed within 36 hours prior to time informed consent was signed, then ECHO does not need to be repeated at Screening. A ±2 day window for Day 7 and Day 14 ECHO.

^jClinical worsening is assessed from Baseline to the conclusion of Day 14 or hospital discharge, whichever comes first. Events occurring after Day 14 will not count towards the primary analysis of clinical worsening.

^k“Prior to wean” assessments will be collected after the dose has been maintained for at least 12 hours and no more than 1 hour prior to beginning to wean study drug. Assessments should be collected for subjects randomized to placebo; PK sample not required in subjects randomized to placebo. In the event that the subject will continue to receive Remodulin beyond Day 28, prior to wean assessments should take place on Day 28.

^lA single PK sample will be collected after 24+6 hours of study drug dosing. The dose should have been maintained for at least 2 hours prior to the sample collection time.

^mConcomitant medications will be captured up to 48 hours after the subject has stopped receiving study drug.

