9.3 PERIOD OF OBSERVATION

For the purposes of this study, the period of observation starts from the time the informed consent is signed and concludes upon meeting screen failure criteria, at the time of death, at the time of hospital discharge, at the time of withdrawal from the study, or at 4 weeks after last dose of study drug, whichever comes first. Day 28 will be considered as the last day of study drug administration for subjects who continue on Remodulin. Subjects with ongoing AEs at the time of hospital discharge will continue to be followed for their AEs until either resolution (or return to normal or Baseline values), until judged by the Investigator to no longer be clinically significant, or until 4 weeks after last dose of study drug. All SAEs should be followed until resolution, death, or the subject is lost to follow-up, even if they are ongoing more than 4 weeks after the last dose of study drug.

If the subject receives commercial Remodulin after hospital discharge, beyond Day 56/End of study, or following withdrawal from the study, AEs/SAEs will be subject to AE/SAE reporting under local government post-marketing AE/SAE reporting requirements.

Supplemental measurements and/or evaluations may be necessary to investigate fully the nature and/or causality of an AE or SAE. This may include additional laboratory tests, diagnostic procedures, or consultation with other healthcare professionals. The eCRF pages should be updated with any new or additional information as appropriate.

If the Investigator detects an SAE in the study subject after the end of the period of observation, and considers the event possibly related to prior study treatment, he or she should contact the Sponsor to determine how the event should be documented and reported.

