8.3 PREMATURE DISCONTINUATION AND MISSING DATA

8.3.1 Missing Data Handling for Primary Efficacy Endpoint

Any subject with a missing value for clinical worsening will be assigned a value of “Yes.”

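### Protocol 8.1 does not separate stopping study drug from leaving the study, so an adverse event can end outcome collection before Day 14, and the documents do not settle how that infant is scored

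*Protocol*

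**What the plan says.** **Withdrawal.** Protocol 8.1 opens with "A subject may be withdrawn from the study and/or study drug by the Investigator at any time for reasons including, but not limited to". The second listed reason is "A serious or life-threatening AE occurs or the Investigator considers that it is necessary to discontinue study drug to protect the safety of the subject". Nothing confines that reason to stopping drug.

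**What study withdrawal ends.** The synopsis says "participation in the study will conclude at the time of hospital discharge, death, withdrawal from the study". Protocol 9.3 closes the observation period "at the time of withdrawal from the study, or at 4 weeks after last dose of study drug, whichever comes first". Sections 3.1 and 3.6 end post-treatment data collection at withdrawal. Table 3-1 footnote n and section 3.3.2.4 end AE recording there.

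**What continues.**
- Section 8.1 asks the investigator, once drug has been given, to try to complete the scheduled evaluations. It also has study drug weaned rather than stopped abruptly.
- Section 7.3.4 schedules a final assessment at withdrawal.
- The synopsis and 3.6 follow AEs that are ongoing at withdrawal.
- Sections 8.1 and 9.3 follow SAEs to resolution, death or loss to follow-up.
- Section 9.3 gives a route to the sponsor for later SAEs judged possibly related.
- Table 3-1 footnote b adds "Day 7 and Day 14 assessments should be performed even if the subject has discontinued study drug". This covers stopping drug, not leaving the study.

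**Endpoint window.** Section 3.3.1.1 contains two windows. Its first sentence assesses worsening at Day 14 or discharge. A later sentence also closes evaluation at discontinuation of study drug. Section 10.3.1 and Table 3-1 footnote j do not have that extra cut-off, and 3.3.1.1.2 and 3.3.1.1.3 count any ECMO start or death in the first 14 days.

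**Analysis.** SAP 8.3.1: "Any subject with a missing value for clinical worsening will be assigned a value of" *Yes*. SAP Table 8-1 censors a subject with no recorded worsening at the last assessment. SAP 10.1.1.3 lists only a Per Protocol analysis and a CDH split, both to be run only if the primary result is significant.

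**The concern.** An infant taken off study drug for an AE is usually still in intensive care, where death, ECMO and added vasodilators are easy to observe. If the same decision also takes the infant out of the study, that information can be lost although it was available.

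The loss is selective, because AEs drive it. The protocol names systemic hypotension as an example of a dose-limiting AE, so losses could well differ between arms.

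Three things are then at stake:
- The primary result depends on a scoring convention in place of an observed outcome.
- New AEs after withdrawal are missing from the safety comparison, possibly while study drug is still being weaned.
- Nothing planned would show how far the convention matters. No sensitivity analysis varies it, and those that exist are not run if the primary test fails. Under SAP 8.4 the secondary tests, including time to clinical worsening, are not run in that case either.

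**Working it through.** **1. Reproduce the planned size.** Inputs (Protocol 10.2, SAP 5): 60% v 30%, one-sided alpha 0.05, power 80%, 1:1 allocation. With pooled rate 0.45:

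n = [1.645·√(2·0.45·0.55) + 0.842·√(0.6·0.4 + 0.3·0.7)]² / 0.30² = 32.9, so 33 per arm.

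The stated 66 reproduces, with normal-approximation power of 80.1%. Exact binomial enumeration of the uncorrected chi-square test at 33 per arm gives 81.2% one-sided and 73.6% two-sided. Both are shown because the sample size is one-sided while SAP 8 and 10.1.1.1 make the test two-sided.

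**2. How one infant can be scored.** Take an infant with no event who is withdrawn from the study for an AE on Day 5 (a hypothetical case).

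| Rule applied | Result |
|---|---|
| SAP 8.3.1, value treated as missing | Worsened |
| SAP Table 8-1, time to worsening | Censored at last assessment |
| Protocol 3.3.1.1, window closes at drug discontinuation | May be entered as not worsened |
| Protocol 10.3.1, window to Day 14 or discharge | True status, if someone collects it |

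**3. If all lost infants are scored worsened.** Let w be the share lost in an arm, p the true event rate, and q the share of lost infants who would have worsened anyway. The scored rate is p + w(1 − q). The documents give no w or q, so all values here are assumptions. With w = 9% on treprostinil and 3% on placebo:

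- Loss independent of outcome (q = p): 0.30 + 0.09·0.70 = 0.363 v 0.60 + 0.03·0.40 = 0.612.
- q = 50% on treprostinil, 60% on placebo: 0.30 + 0.09·0.50 = 0.345 v 0.612.
- q = 80% in both arms: 0.30 + 0.09·0.20 = 0.318 v 0.60 + 0.03·0.20 = 0.606.

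| Assumption | Exact two-sided power |
|---|---|
| No loss | 73.6% |
| 9% v 3%, q = 80% | 70% |
| 9% v 3%, q = 50% / 60% | 63% |
| 9% v 3%, q = p | 57.6% |
| 6% v 3%, q = p | 64.5% |
| 15% v 3%, q = p | 43.7% |

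One-sided, 9% v 3% with q = p moves power from 81.2% to 67.2%.

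**4. A single table.** The planned rates correspond to about 10/33 v 20/33. Rescoring event-free treprostinil infants as worsened gives (uncorrected chi-square):

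| Treprostinil events | Two-sided p | One-sided p |
|---|---|---|
| 10 | 0.013 | 0.007 |
| 11 | 0.026 | 0.013 |
| 12 | 0.049 | 0.024 |
| 13 | 0.085 | 0.042 |
| 14 | 0.139 | 0.070 |

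**5. The bias can run the other way.**
- Loss on placebo, scored worsened: with a true rate of 60% in both arms and 10% lost on placebo only, placebo is scored 0.60 + 0.10·0.40 = 64%. The exact chance of a two-sided result favouring treprostinil rises from 3.0% to 5.9%.
- Loss scored as not worsened: the scored rate is p − wq. At 9% v 3% with q = 80%, it is 0.30 − 0.072 = 0.228 v 0.60 − 0.024 = 0.576. The difference is 34.8 points against a true 30.

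**The case against.** The strongest reply is that 8.1 already deals with these infants. Its request to complete scheduled evaluations directly follows the sentence on premature discontinuation from the study, so it is the specific provision for them. That stands: the provision has effect and should not be read away. It remains a request to try. It does not name ECMO, added-vasodilator or vital status at Day 14, and it sits beside rules that end participation at withdrawal.

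Four stronger readings are tempting, and the documents do not support them.

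- *Every AE withdrawal becomes an efficacy failure.* SAP 8.3.1 acts only on a missing value. Status is read from a case report form page (SAP 10.2.5), and under the later sentence of 3.3.1.1 a site could enter a valid *No*.
- *Harms and deaths after withdrawal are lost.* Known SAEs are followed to their end, ongoing AEs are followed, there is a final assessment, and later possibly related SAEs have a reporting route. The gap is new events after withdrawal, chiefly those that are non-serious or judged unrelated.
- *The AE follow-up sentence in 8.1 contradicts the Day 14 assessments.* That sentence ("the subject will be followed until either the Investigator determines that the AE has resolved, it is no longer considered clinically significant") can be read as governing follow-up of the AE, and Table 3-1 footnote b and 7.3.2.1 separately require Day 7 and Day 14 assessments after drug stops. The two are compatible.
- *Three withdrawals overturn the trial.* They do so only on the SAP's two-sided test. At the protocol's one-sided 0.05 the same table gives p = 0.042, and four are needed.

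It is also fair to say that loss independent of outcome is the harsher assumption. Ventilated infants withdrawn for serious AEs may well have worsened anyway, so the power range is reported in place of a single figure.

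**Conclusion.** The concern holds as a gap in wording with statistical consequences, and it should be fixed. An AE can end study participation under 8.1. New AEs then go unrecorded, and the Day 14 outcome is protected only by an effort clause. A missing outcome is scored as worsened in the primary analysis and censored in the time-to-event analysis, and the conflicting window in 3.3.1.1 could instead yield *No*. The direction of bias is therefore not fixed.

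At assumed losses of 9% v 3%, all scored worsened, exact two-sided power falls from 74% to between 58% and 70%. These figures rest on assumed withdrawal rates and on an assumed link between withdrawal and outcome. The allowance from 66 evaluable to 70 randomized (4/70 = 5.7%) is not attributed to any cause and cannot supply the rates.

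**What to change.** 1. In Protocol 8.1, separate discontinuation of study drug (AE and safety reasons) from withdrawal from the study (for example parental withdrawal, or never dosed). This changes what is recorded, not when or how drug is stopped.
2. State that infants who stop drug stay in the study. Collect ECMO, added-vasodilator and vital status to Day 14 or discharge, and record AEs to the usual 9.3 end, including during any wean.
3. When a parent withdraws the infant, ask permission to take Day 14 status from the chart.
4. Reconcile the window in 3.3.1.1 with 10.3.1 and Table 3-1 footnotes b and j. Align the end-of-observation wording in the synopsis, 3.1, 3.6, Table 3-1 footnote n, 3.3.2.4 and 9.3.
5. In the SAP, add a sensitivity analysis that varies the missing-as-worsened rule. Run it whether or not the primary test is significant.

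The cost is protocol and SAP wording plus one analysis. No visits are added, because the infants are usually still in hospital and the Day 7 and Day 14 assessments are already scheduled after drug is stopped.

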8.2 CRITERIA FOR TERMINATING THE STUDY

The study may be stopped at any time if, in the opinion of the Investigator and/or Sponsor, continuation of the study represents a serious medical risk to the subjects. This may include, but is not limited to, the presence of serious, life-threatening, or fatal adverse events or AEs that are unacceptable in nature, severity, or frequency. The Sponsor reserves the right to discontinue the study for any reason at any time.

8.3 CRITERIA FOR DISCONTINUING A SITE

The study may also be terminated at a given center if:

- The Principal Investigator elects to discontinue the study.
- The Sponsor elects to discontinue the study at the site.
- US FDA, European, or national regulations are not observed.
- The protocol is repeatedly violated.
- Changes in personnel or facilities adversely affect performance of the study.

9 ADVERSE EVENT REPORTING

9.1 DEFINITIONS

9.1.1 Adverse Event (AE)

An AE is any untoward medical experience occurring to a subject whether or not it is related to the use of the study drug. An AE may include an intercurrent illness, injury, or any other concomitant impairment of the subject's health, as well as abnormal laboratory findings if deemed to have clinical significance. AEs may also include worsening of an existing symptom or condition or post-treatment events that occur as a result of protocol-mandated procedures.

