3.3.2.4 Adverse Events (AEs)

Documentation of AEs will be recorded in the eCRF from the time informed consent is provided until time of screen failure, time subject is withdrawn from study, time of hospital discharge, death, or until 4 weeks after the last dose of study drug, whichever comes first. All AEs should be followed until either resolution (or return to normal or Baseline values), until judged by the Investigator to no longer be clinically significant or until 4 weeks after last dose of study drug. Subjects with ongoing AEs at the time of hospital discharge will continue to be followed for their AEs until either resolution (or return to normal or Baseline values), until judged by the Investigator to no longer be clinically significant, or until 4 weeks after last dose of study drug. All SAEs will be followed until resolution, death, or the subject is lost to follow-up, even if they are ongoing more than 4 weeks after the last dose of study drug. Sections [9](#) and [15.1](#) provide the definitions and guidelines for recording AEs. If the subject receives Remodulin after hospital discharge, beyond Day 56/End of study, or following withdrawal from the study, AEs/SAEs will be subject to AE/SAE reporting under local government post-marketing AE/SAE reporting requirements.

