15 APPENDICES

15.1 GUIDELINES AND DEFINITIONS FOR RECORDING ADVERSE EVENTS

For each adverse event, the Investigator will: (1) rate the intensity and seriousness of the AE, (2) estimate the causality of the AE to study drug, and (3) note actions taken to counteract the AE.

Definitions of Intensity, Seriousness, Causality, and Action Taken

Intensity

An assessment of the relative intensity (severity) of an AE is based on the investigator's clinical judgment. The maximum intensity encountered during the evaluation period should be checked. The assessment of intensity should be independent of the assessment of the seriousness of the AE.

- Mild: No limitation of usual activities.
- Moderate: Some limitation of usual activities.
- Severe: Inability to carry out usual activities.

Difference Between "Severe" and "Serious"

The term "severe" is often used to describe the intensity (severity) of a specific event (as in mild, moderate or severe myocardial infarction); the event itself; however, may be of relatively minor medical significance (such as severe headache). This is not the same as "serious", which is based on the outcome or action criteria usually associated with events that pose a threat to life or functioning. Seriousness (not severity) serves as a guide for defining regulatory reporting obligations.

Causality

An estimate of causality between a specified AE and the study drug is made by the Investigator.

Definitions of the categories follow:

- POSSIBLE - the AE MAY have been caused by study drug. There is a reasonable causal relationship between the study drug and the SAE. The event responds to dechallenge. Rechallenge is not required.
- PROBABLE - it is LIKELY that the AE was caused by study drug. There is a reasonable causal relationship between the study drug and the SAE. Dechallenge information is lacking or unclear.
- NOT RELATED - it is UNLIKELY that the AE was caused by study drug. There is not a temporal relationship to study drug administration (too early, or late, or study drug not

taken), or there is a reasonable causal relationship between another drug, or concurrent disease and the SAE.

Action Taken with Test Agent*

The action taken with test agent as a direct result of the AE:

- DOSE NOT CHANGED - there was no alteration in either the dose or regimen of the test agent
- DOSE INCREASED – dose was increased
- DOSE DECREASED – dose was decreased

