- DRUG INTERRUPTED - the dose or regimen of the test agent was altered or administration of the test agent was stopped temporarily
- DRUG WITHDRAWN- administration of the test agent was stopped permanently and not restarted. This does not apply if the subject was on drug at the time of death. For this scenario “Dose not changed” would be marked.
- Not Applicable- (i.e., AE occurred prior to administration of test agent)

* Only the last action should be recorded on the CRF.

Outcome

- Fatal – The study subject died
- Not Recovered/Not Resolved – The AE was ongoing at the end of the study/AE observation period
- Recovered/Resolved – The AE resolved
- Recovered/Resolved with Sequelae – The AE is considered resolved; however, there is a residual sequelae
- Recovering/Resolving – The AE is improving but is not yet completely recovered/resolved at the end of study/AE observation period
- Unknown – The outcome of the AE cannot be determined

AE/SAE Start Date verses Serious Date

The AE start date is classified as the first day the subject experiences sign and symptoms of an event and should be entered on the eCRF and SAE Notification Form section “Onset date of symptoms.” The date the event became serious is the first day the event meet one of the serious criterion (see section 9.1.2). The start date and date event became serious could be the same date (e.g., clavicle fracture from a fall).

Note: The start date (onset) should never be a date prior to the subject signing the informed consent.

AE/SAE Stop Date

For AEs and SAEs the dates listed on the eCRF and SAE Notification Form will always be the same. For non-fatal events, this is the date the last sign and/or symptom resolved. For fatal events this is the date of Death. If the event Recovered/Resolved with Sequelae enter the date the subject's medical condition resolved or stabilized.

For SAEs follow-up must continue until resolution, death, end of study, or subject is lost to follow-up.

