12.2 ADVERSE EVENTS

All AEs will be coded to PT and SOC using the latest version of the MedDRA coding dictionary. Treatment-emergent adverse events (TEAEs) are those AEs with onset date equal to or after the start date of the study drug. TEAEs will appear in listings and summaries. Non-treatment-emergent AEs (the AEs occurring after signing the Informed Consent Form (ICF), but before receiving study drug) will be listed, but will not be included in summary tables.

The AE listings will include the AE verbatim term and its corresponding PT and SOC, all eCRF details, and a treatment-emergent indicator flag. The following AE listings will be provided:

- All AEs
- Deaths
- SAEs
- AEs leading to permanent discontinuation of study drug

All AE summaries will be sorted by overall frequency and/or SOC and will include the number and percentage of subjects experiencing each type of AE, the total number of each type of AE, and the AE rate of each type of AE. AE rate will be calculated as the total number of AEs divided by the total patient days of exposure to study drug per treatment group.

The following AE summaries will be provided:

- AEs by SOC and PT
- AEs by PT
- Deaths
- SAEs by SOC and PT
- Non-serious AEs by SOC and PT
- AEs probably or possibly related to study drug by SOC and PT
- AEs leading to permanent discontinuation by PT
- AEs by SOC, PT, and severity (mild, moderate, severe)

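### The SAP's treatment-emergent rule has no clause for worsening, so an AE that starts after consent on a day before first dose and turns severe, serious or fatal on study drug can be missing from the AE summary tables

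*Protocol*

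**What the plan says.** Protocol 3.3.2.4 starts AE collection before dosing: "Documentation of AEs will be recorded in the eCRF from the time informed consent is provided". Protocol 9.1.1 adds that "AEs may also include worsening of an existing symptom or condition". Protocol 10.3.3 promises the incidence of treatment-emergent AEs but does not define the term.

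The definition is in SAP 12.2: "Treatment-emergent adverse events (TEAEs) are those AEs with onset date equal to or after the start date of the study drug". An AE that falls after consent "but before receiving study drug) will be listed, but will not be included in summary tables". The summaries listed in that section include deaths, SAEs, AEs related to study drug and AEs by severity. None is exempted from the rule, and no clause covers an AE that worsens after dosing.

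How an AE is dated and graded is set in Protocol Appendix 15.1:

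- Start: "The AE start date is classified as the first day the subject experiences sign and symptoms of an event". The start may not precede consent.
- Intensity: "The maximum intensity encountered during the evaluation period should be checked".
- Seriousness has its own date: "The date the event became serious is the first day the event meet one of the serious criterion".
- The stop date of a fatal event is the date of death.

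**The concern.** The rules of Appendix 15.1 describe an event that keeps its first start date while its intensity and seriousness are updated. The SAP then sorts that event by its start date only. Suppose mild hypotension or minor bleeding begins after consent on the evening before dosing and becomes severe, serious or fatal during the infusion. On the record it is a pre-dose AE with a high maximum intensity, and the SAP would list it without summarizing it.

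Safety is part of the primary objective (Protocol 2.1). Protocol 1.2 describes the drug as a systemic as well as pulmonary vasodilator and an inhibitor of platelet aggregation. The entry criteria exclude uncontrolled hypotension and clinically significant bleeding at Screening, but milder forms can be present at entry. Aggravation of such a problem on drug is a harm that the summaries should be able to show.

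**Working it through.** The SAP states no figure on this point, so the check is to apply its rule to test cases.

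**Inputs.** Onset-date rule and exclusion of pre-dose AEs: SAP 12.2. Start date, maximum intensity, serious date and stop date: Protocol 15.1. Collection from consent: Protocol 3.3.2.4. Planned arm size of 33: Protocol 10.2 and SAP 5.

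**Rule.** An AE is treatment-emergent if its onset date is on or after the date of first dose. For illustration, take first dose at 02:00 on day 2.

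| Case | Onset | By the onset-date sentence | By the pre-dose sentence | Summarized? |
|---|---|---|---|---|
| A. Starts after consent the evening before, kept as one record, turns severe, serious or fatal on drug | Day 1, 22:00 | Not treatment-emergent | Pre-dose | No |
| B. Starts on the dosing day, before the dose | Day 2, 01:00 | Treatment-emergent | Pre-dose | The two SAP sentences disagree |
| C. Worsening entered as a new AE | Day 3, 05:00 | Treatment-emergent | Not pre-dose | Yes |
| D. Condition present before consent, worsens on drug | Start of the worsening | Treatment-emergent | Not pre-dose | Yes |

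The gap is case A. Whether a worsening event is handled as A or C depends on how the site enters it, and neither document gives an instruction.

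Case B matters for the repair. Protocol 9.2 collects onset time as well as date. If the SAP moved to date and time without a worsening clause, case B events would join case A in the excluded group.

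**Size.** One infant in a planned arm of 33 is 1/33 = 0.0303, or 3.0 percentage points. If about 70 are randomized and all are dosed, an arm has 70/2 = 35 and one infant is 1/35 = 2.9 points. These are upper limits per omitted infant. An any-SAE or any-severe-AE row falls only if the infant has no other qualifying treatment-emergent event, and the death row only if no other fatal AE record for that infant qualifies. The documents give no count of case A events.

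**The case against.** The strongest reply is that one record per event is an inference. No sentence in Appendix 15.1 says so, and none forbids a new entry when an event worsens. Protocol 9.1.1 allows worsening to be an AE in its own right; such an AE first shows signs after dosing and is summarized (case C). A reader might infer that Protocol 9.1.1 and SAP 12.2 contradict each other, or that every such event is certain to be excluded. The documents do not support either reading. They leave recording practice unstated, and the summaries then depend on it.

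The set is also narrow. A reader might infer that pre-existing instability in general is lost once it worsens, but conditions present before consent are not affected (case D), and the onset-date sentence keeps dosing-day onsets in. What remains is AEs starting after consent on an earlier calendar day. Protocol 7.2 asks for study drug as soon as possible after randomization, so the window is usually short.

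The events are not hidden. SAP 12.2 lists all AEs, deaths and SAEs with a treatment-emergent flag. Deaths through Day 14 count in the primary endpoint whatever the AE onset. Disease-related events have their own summary with no stated onset filter (SAP 12.4.3), and vital signs and platelets are summarized as change from Baseline. Safety analysis is descriptive, and about 70 infants can be read line by line.

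All of this stands, and it limits the frequency and the consequence. It does not supply what the tables would lack: by-arm counts of SAEs, severe AEs and related AEs that include these events. The table of deaths might be built from death records, but SAP 12.2 places it among the AE summaries without saying so.

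**Conclusion.** The point holds in a limited form. As written, SAP 12.2 can leave out of the AE, SAE, severity, related-AE and death summaries an AE that starts after consent on a calendar day before first dose and then increases in intensity, becomes serious or becomes fatal on study drug. This assumes that the site keeps one record with its first start date, which Appendix 15.1 suggests but does not state.

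The number affected is probably small and cannot be estimated from the documents. Each omitted infant moves a row by at most 3.0 percentage points of a planned arm of 33, under the condition shown in the working. A reader might multiply this up to several infants per arm, but nothing in the documents supports such a count.

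A reader might also infer that the tables would favor the drug. Within one arm an omission can only lower the count, but it can happen in either arm, so the direction of the between-arm effect is unknown.

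The change is worth making before unblinding because it is cheap and the rule, as it stands, can give a wrong count of serious outcomes.

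**What to change.** **SAP 12.2, definition.** Define a treatment-emergent AE as one with onset at or after first dose, or one with earlier onset that increases in intensity, becomes serious or becomes fatal after first dose. If onset is compared by date and time, adopt the worsening clause in the same edit.

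**SAP 12.2, deaths and SAEs.** State that these summaries include every death, and every event becoming serious, after first dose, whatever the onset date. Use the date of death and the date the event became serious. Protocol 15.1 defines the latter, but the documents do not clearly say that the eCRF holds it: Protocol 9.2 names seriousness among the eCRF items and no serious date. Name the source, either the eCRF or the SAE Notification Form.

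**Recording.** Maximum intensity alone cannot date a non-serious worsening. Add to the eCRF completion guide that a post-dose increase in intensity of a pre-dose AE is entered as a new record linked to the first. Add to the SAP that linked records count as one episode. Otherwise the wider definition and the new record could count the same worsening twice in the event totals and the AE rate.

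**Cost.** A short SAP edit, a small data-entry instruction, and a few more events in the tables. Placing the instruction in the completion guide avoids editing Protocol 15.1, which would need the approvals that Protocol 13.1 requires for amendments. No test, sample size or clinical rule changes.
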